#### **Data**

For completeness and clarity it is worth briefly overviewing the data that will be available and the timing of data collection. More details can be found in the pilot report, with a copy of all questionnaires and of the session form available in Annex E of that report.

LA Workbook: Spreadsheet to be filled out by the SPOC/Data Lead of the Local Authority to provide background information about the young person, as well as a log of training dates for practitioners involved in the study and a log of clinical supervision sessions. The background information about the young person includes: date of birth, gender, ethnicity, SEN status, reason for referral into the service and any other services the young person is involved with. The workbook also includes a tab to list some basic demographic information (ethnicity, gender, age) about the young people who were approached to enter the study but who did not consent to and provides an option to explain the reason (if known) for non-consent.

Baseline young person questionnaire: The baseline young people survey is administered shortly after recruitment, in week 1, during a session with the assigned practitioner. It includes the Strengths and Difficulties Questionnaire (SDQ), a scale developed by the evaluation and project team about the young person's safety (young person Checkpoint), the Social Connectedness Scale — Revised (SCS-R), the Pro-Social IDentity Scale (PIDS) and a question about the young person's main activity at the time of the survey.

Baseline practitioner questionnaire: The baseline practitioner survey is completed shortly after recruitment, in week 1. It asks the young person's practitioner to report their risk rating of the young person, as well as their perception of the young person's safety using the practitioner version of Checkpoint.

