Endline young person questionnaire: The endline young people survey is administered at the end of Your Choice period, in week 20 after recruitment, during a session with the assigned practitioner. It includes the same content as the baseline young person questionnaire, plus the following scales: The Short Warwick–Edinburgh Mental Well-being Scale (SWEMWBS), the Trait Emotional Intelligence Questionnaire – Adolescent Short Form (TEIQUE-ASF) – Self regulation subscale, and the Pro-Social IDentity Scale (PIDS). The latter were excluded from the baseline survey to keep it as short as possible while focusing on the most relevant measures, and also because these scales are most interesting as outcomes rather than as conditioning variables given the rich data we already collect at baseline. The endline questionnaire also asks the young person some questions about their experience working with their practitioner: it asks whether they would recommend it to someone else, it provides a free text box for any additional comments, and it asks a series of 7 questions about the practitioners' approach and practices to working with the young person. These approaches/practices were selected to be those most characteristic of the practices embedded in the Your Choice training.

Endline practitioner questionnaire: The endline practitioner survey is completed at the end of Your Choice period, in week 20 after recruitment. It includes the practitioner version of Checkpoint, as well as a series of 7 questions about the practitioners' approach and practices to working with the young person. These approaches/practices are the same as the ones asked to the young person in the endline questionnaire and were selected to be those most characteristic of the practices embedded in the Your Choice training.

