Session forms: Practitioners are requested to fill out a session form every time they conduct a session with the young person or every time a session is cancelled. The session form asks a few details about the location of the session, the young person's level of engagement, whether the session was related to the Your Choice programme, and depending on the latter offers one or two dropdown menus to describe the content of the session. The practitioner is then offered a free text box to include any further comments on the session. If the session did not take place, the session form asks whether the reason for cancellation is known and offers a free text box to include any other details about the session that did not take place.

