#### Compliance

In the Your Choice trial, compliance is defined at three levels: LA, team and young person.

At the LA level, where randomisation is to be implemented within LA across teams:

- That the assignment of young people to trained and control teams is not selective on the young person's characteristics or aspects of their case. As mentioned below, we will not be able to fully rule out selective assignment of young people to teams, but we will obtain quantitative and qualitative evidence to support any claims of nonselective assignment – in particular, we expect to see balanced distribution of observed characteristics;
- That trained and control teams undertake similar efforts to recruit young people to participate in the trial hence we would expect to see similar consent rates into treated and control teams.

At the team level, the following criteria define compliance:

- That in teams randomised to deliver Your Choice, all practitioners receive training (and when a new practitioner enters the team, they receive training to deliver Your Choice);
- That in teams randomised to the control group, no practitioner receives training;
- That trained practitioners intend to meet three times a week with the young people enrolled in Your Choice for 12 weeks (over the course of 12-18 weeks)
- That trained practitioners meet at least monthly with their clinical supervisor to discuss progress and the cases assigned to them;
- That control teams do not deliver elements of Your Choice in their interactions with young people assigned to them (other than what they would do in regular BAU;

At the young person level, the following criteria define compliance with the trial protocols:

- That the young person is not transferred across trained and control teams while participating in the programme;
- The young person undertakes the intended programme of support with the Local Authority and does not drop out of this programme prematurely
- That young people in the Your Choice meets 3 times a week with their practitioner for 12 weeks (over the course of 12 to 18 weeks)
- That the young person completes the planned surveys.

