Information on compliance: Compliance with the randomisation of teams will be directly observed in the administrative data provided by the Local Authorities about the names and teams of practitioners involved in the study and their date of training if relevant. Information collected in session forms will reveal adherence to the delivery of Your Choice or BAU across teams, as well as violations to the rule that young people should not be re-allocated to other teams during the participation period. Qualitative data will be collected from a subsample of practitioners and clinical leads, to inform on the frequency and content of meetings between practitioners and their clinical supervisors. The baseline questionnaire will provide information to test for the presence of systematic differences between young people assigned to treated and control teams, either due to non-random allocation of young people

to teams or to differential selectivity in young people across treatment arms who agree to share their data (we will not be able to distinguish between the two sources of bias).

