We will further extend our analysis by using an Instrumental Variable (IV) approach to give an indication of the effects a) of receiving Your Choice and b) of the intensity of treatment. To implement a) and b), we will use a Two Stage Least Squares (2SLS) approach with group allocation as the instrumental variable for compliance. In a), we will define compliance as a binary indicator that takes the value 1 if the young person receives any of the Your Choice programme and 0 otherwise. In b), we will define compliance as a continuous variable measuring the proportion of Your Choice sessions that the young person received out of the total planned for participants (=12x3). The first stage will model the compliance variable using the same explanatory variables used for the headline ITT analyses and the instrument. The second stage model will use predicted compliance in place of the group identifier variable in the ITT analyses specified above to generate Complier Average Causal Effect (CACE) estimates.

At the practitioner level – practitioners are supposed to received 3 + 1 days of training and to receive clinical supervision at least once monthly. Using information from the workbook on training and clinical supervision sessions, we will document the extent to which this happened across teams involved in the trial. We will not take this form of compliance into consideration in the estimation of the treatment effects.

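### Session-form content fields depend on an unblinded practitioner's Your Choice label, so the planned between-arm comparison of content may partly reflect the form; seven practice items with no such filter described are collected but not analysed

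*Protocol*

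**What the plan says.** The Protocol's Data section describes the session form. It asks if the session had anything to do with Your Choice. The content fields come next and turn on that answer: the form "depending on the latter offers one or two dropdown menus to describe the content of the session". A field that does not depend on the answer follows: "The practitioner is then offered a free text box to include any further comments on the session". The form itself is not reproduced; the same section refers to a "copy of all questionnaires and of the session form available in Annex E of that report", meaning the pilot report.

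Practitioners in both arms complete the form (Protocol, Implementation and process evaluation, Research methods). Several planned uses depend on it:

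- The Compliance section states: "Information collected in session forms will reveal adherence to the delivery of Your Choice or BAU across teams". One team-level criterion is "That control teams do not deliver elements of Your Choice in their interactions with young people assigned to them", with an exception for what they would do in regular BAU.
- Step 2 of the Protocol's Analysis checks that programme-specific content was received in the Your Choice arm and not in the control arm, and makes all later interpretation rest on that check.
- The process evaluation compares number and type of sessions between arms. Session forms are its only survey source in Table 8.
- The SAP section on descriptive analysis of intervention content covers content in both arms.

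Separately, the Data section says that the endline young-person and practitioner questionnaires each hold seven questions on the practitioner's approach and practices. These were "selected to be those most characteristic of the practices embedded in the Your Choice training".

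**The concern.** A comparison of content between arms needs the same question put in the same way in both. Here the content fields that appear depend on an answer given by someone who knows the arm. If that answer tracks the arm, two things can follow. A difference in recorded content can arise without a difference in practice. And a control practitioner who uses Your Choice-type techniques without calling them that may leave no record comparable with the treated arm.

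This matters most for a null result. The evaluators would want to know whether the programme had no effect or whether control practice came close to it. Session-form content alone may not separate the two, and the plan names no other between-arm measure of content.

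**Working it through.** The plan gives no figure on this point, so there is none to reproduce. The check sets the passages side by side.

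**1. What the branching implies.** There are two answers, and the number of menus is one or two depending on the answer. One answer therefore opens more menus than the other, and under any layout at least one menu is recorded for only one answer. The text does not say which answer opens two, what each menu lists, or whether one menu is common to both.

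**2. Does the label follow the arm?** The Randomisation section says practitioners know their team's status. Only treated teams are trained. No passage pre-fills the answer or reserves yes for trained teams. That label and arm move together is therefore a reasonable inference, not a stated fact.

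**3. Consequence in symbols.** Let q be the true share of sessions using a given technique, equal in both arms, and let L1 and L0 be the shares of treated and control sessions labelled Your Choice. Assume that labelling is unrelated to the technique within an arm.

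- Technique listed only after a yes: the recorded shares are q × L1 and q × L0. The recorded contrast is q × (L1 − L0), although the true contrast is zero. In the control arm, a share q × (1 − L0) of sessions goes unrecorded.
- Technique listed on a menu shown to everyone: the recorded contrast is q − q = 0.

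The documents give neither q, L1, L0 nor the layout, so no number follows.

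**4. What the other sources cover.**

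- Number and duration of sessions, location and engagement are not described as depending on the label, but they do not measure content.
- Training logs show who was trained, not what untrained staff deliver.
- The qualitative work focuses on the Your Choice arm. Free-text responses enter the thematic analysis, but no comparison of them between arms is set out.
- The seven endline items concern practice directly, and no filter on the label is described for them.

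**5. Are the seven items used?** They appear in none of the Protocol's Analysis steps, nor in its process evaluation analysis, nor in the SAP. The introduction to the SAP's Analysis section mentions practitioner-level outcomes, but its example is the assessment of needs and risks.

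**The case against.** The strongest reply is that the form is in an annex not available here, and that every session gets at least one content menu. If that menu is common to both answers and includes CBT-type items, comparing arms on it is sound. This stands, and it is why no size is claimed.

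A second reply is that similar techniques in control teams need not be contamination. This also stands: the criterion exempts regular BAU, and the Protocol says BAU varies in intensity and technique. The items would describe control practice; they would not by themselves show a breach.

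A third is that the practice items have faults of their own. Practitioners reporting on themselves are unblinded, and young people answer in a session with the practitioner. The items exist only for endline completers: 30% attrition is assumed, a footnote to the sample size section puts pilot attrition at 54%, and the Protocol reports weaker adherence to data collection in pilot control teams. These faults are real. They argue for using the items beside the session forms, not in their place, and do not justify leaving them unanalysed.

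A reader might also infer that the label feeds the complier average causal effect (CACE), whose binary compliance variable "takes the value 1 if the young person receives any of the Your Choice programme and 0 otherwise". The SAP does not say so. It names only monitoring data, and describes control crossover as support from a trained practitioner in another team, which practitioner names and training dates can help identify. Counting similar techniques in controls as receipt would change the estimand.

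**Conclusion.** The point holds in a limited form. Part of the session-form content record depends on an unblinded practitioner's label, yet the between-arm content and adherence comparisons rest mainly on that form. Recorded content may therefore differ by arm partly because of the form, and unlabelled Your Choice-type content in control teams may be missed. This assumes that control practitioners seldom answer yes and that some relevant items sit on the label-dependent menu. Neither can be confirmed from the documents, so the size is unknown.

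A reader might go further and infer that the form guarantees a content contrast, or that a null result caused by similar control practice could never be recognised. The documents support neither. The menu contents are unseen, and the seven items would provide relevant evidence once analysed. The primary ITT estimate is unaffected in every case; only the evidence for interpreting it is weakened.

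**What to change.** In the SAP section on descriptive analysis of intervention content, and in Step 2 of the Protocol's Analysis:

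- Pre-specify a comparison by arm of the seven endline practice items, young-person and practitioner versions, as a label-free check of treatment contrast and control-arm practice alongside the session forms. Use the ITT model with LA fixed effects and LA-clustered standard errors. The items are not listed in the baseline questionnaires, so the baseline-outcome term drops out. State whether items are reported singly or as one score.
- Limit between-arm session-form comparisons to fields offered whatever the label: number, duration, location, engagement and any common menu. State which menu, if any, is common.
- Describe the label-dependent menu in the treated arm only.

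The CACE definition need not change. The cost is SAP wording and one extra table, with no new data collection. The limits of the items (self-report, the practitioner's presence, endline completers only) should be stated beside the results.

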#### Compliance

In the Your Choice trial, compliance is defined at three levels: LA, team and young person.

At the LA level, where randomisation is to be implemented within LA across teams:

- That the assignment of young people to trained and control teams is not selective on the young person's characteristics or aspects of their case. As mentioned below, we will not be able to fully rule out selective assignment of young people to teams, but we will obtain quantitative and qualitative evidence to support any claims of nonselective assignment – in particular, we expect to see balanced distribution of observed characteristics;
- That trained and control teams undertake similar efforts to recruit young people to participate in the trial hence we would expect to see similar consent rates into treated and control teams.

At the team level, the following criteria define compliance:

- That in teams randomised to deliver Your Choice, all practitioners receive training (and when a new practitioner enters the team, they receive training to deliver Your Choice);
- That in teams randomised to the control group, no practitioner receives training;
- That trained practitioners intend to meet three times a week with the young people enrolled in Your Choice for 12 weeks (over the course of 12-18 weeks)
- That trained practitioners meet at least monthly with their clinical supervisor to discuss progress and the cases assigned to them;
- That control teams do not deliver elements of Your Choice in their interactions with young people assigned to them (other than what they would do in regular BAU;

At the young person level, the following criteria define compliance with the trial protocols:

- That the young person is not transferred across trained and control teams while participating in the programme;
- The young person undertakes the intended programme of support with the Local Authority and does not drop out of this programme prematurely
- That young people in the Your Choice meets 3 times a week with their practitioner for 12 weeks (over the course of 12 to 18 weeks)
- That the young person completes the planned surveys.

Information on compliance: Compliance with the randomisation of teams will be directly observed in the administrative data provided by the Local Authorities about the names and teams of practitioners involved in the study and their date of training if relevant. Information collected in session forms will reveal adherence to the delivery of Your Choice or BAU across teams, as well as violations to the rule that young people should not be re-allocated to other teams during the participation period. Qualitative data will be collected from a subsample of practitioners and clinical leads, to inform on the frequency and content of meetings between practitioners and their clinical supervisors. The baseline questionnaire will provide information to test for the presence of systematic differences between young people assigned to treated and control teams, either due to non-random allocation of young people

to teams or to differential selectivity in young people across treatment arms who agree to share their data (we will not be able to distinguish between the two sources of bias).

#### **Analysis**

Our primary analysis uses only randomised teams during the Home Office, pilot and efficacy phases. It will involve various steps.

Step 1. Thorough check that the group of young people assigned to Your Choice appear to come from the same population as those assigned to the control group along many observed variables describing demographic characteristics (e.g. gender, age, ethnicity, etc), main activity at baseline (education or training, employment, other), whether looked after, special education needs, primary needs for Local Authority support (e.g. abuse, disability, family acute stress, etc), various measures observed in the baseline youth survey including SDQ scores and self-reported risk assessment, practitioner risk assessment from baseline practitioner questionnaire. We will also check that the distribution of services to which young people have been assigned look balanced across experimental arms. All subsequent analysis addressing the key research questions set out earlier in this document must rely on a good understanding of the comparability between the treated and control groups.

Step 2. Thorough check of the delivery of Your Choice in contrast with BAU, revealing the extent to which the programme effectively changes interactions between the youth workers and young people and characterising the intensity of treatment for different groups. Specifically, we will check that young people assigned to Your Choice received an intensive schedule of meetings with content that is specific to the programme (hence matching the Your Choice protocol), while young people assigned to the control teams did not. Again, all subsequent analysis and interpretation of findings must rely on a good understanding of what the programme delivers in comparison with BAU.

Step 3. Main analysis, which will be a linear probability model to measure the impact of Your Choice on an indicator for high to very high conduct problems (primary outcome). The regression will also control for the baseline outcome and any controls for which we find statistically significance imbalances in step 1, as well as Local Authority fixed effects. Standard errors will be clustered at the Local Authority level, following Chaisemartin and Ramirez-Cuellar (2022). Effects will be shown in percentage points and as a percent change relative to the baseline average frequency of young people in the high to very high range for this population. We will show the 95% confidence interval for the estimated effect. This analysis will directly address research question 1.

Step 4. Robustness analysis of estimated effects on primary outcome. This will involve estimating alternative versions of the primary regression model using a post-double selection

LASSO to identify variables that are related with both the treatment status and the primary outcome. We will consider relevant contextual, demographic, personal and environmental information as described in step 1. This analysis will provide further support for the findings in the main analysis (step 3).

Step 5. Steps 3 and 4 will be repeated for the secondary outcomes measuring whether the young person got arrested at any point during the 16 months following recruitment into Your Choice (PNC data), and risk assessments by the young person and practitioner at endline (survey completed at week 20 after recruitment). Effects on arrest probabilities will be shown in percentage points and as a percent change relative to frequency of arrests among the control group over the same period. Effects on risk levels will be shown in standard deviation units. Standard errors will be clustered at the local authority level and we will show the 95% confidence interval for the estimated effect. This analysis will address research question 2.

Step 6. Investigation of potential mechanisms through which Your Choice affects externalising behaviour, arrests or risk assessment. We will regress each of the other secondary outcomes measured at endline (week 20 after recruitment) on a treatment indicator, the baseline value of that variable where available, other observed characteristics where imbalances at baseline were found (steps 1 and 2), and local Authority fixed effects. This will provide suggestive evidence on potential mechanisms underlying identified responses in externalising difficulties and criminal behaviour and risk, as detailed in the Logic Model. Effects will be shown in standard deviation units. Standard errors will be clustered at the local authority level and we will show the 95% confidence interval for the estimated effect. This analysis addresses research question 3. We will not run a fully fleshed mediation analysis because we do not have exogenous variation to independently vary the mediators.

Step 8. Heterogeneity analysis of the impact of Your Choice on the primary outcome (conduct problems) and criminal activity (possibility of arrest). This will be carried out by adding interaction terms between the treatment indicator and variables describing key demographic and contextual factors. Specifically, we will interact the treatment indicator with age, gender, ethnicity, special education needs and practitioner risk assessments at baseline. This analysis will address research question 4.

15

